**Study Implementation:**

Couples planning in vitro fertilization (IVF) with intent for blastocyst culture for preimplantation genetic screening (PGS) will be offered enrollment prior to initiation of their treatment cycle. Ovarian stimulation will be performed with standard treatment chosen by the couple's primary physician. The day of ovulation trigger will be determined by the primary physician. Oocyte retrieval will be performed according to clinic standard 36 hours following ovulation trigger. All oocytes aspirated from the left ovary will be allocated to Global Media while all oocytes from the right ovary will be allocated to SAGE media (see supplement with media systems). Follicular fluid will be collected from a large and a medium-sized follicle from each ovary in order to perform a direct correlation of follicular size to oocyte recovery, maturation, and embryo development. The collected follicular fluid will also be assayed for estradiol, follicle stimulating hormone, leutinizing hormone, and progesterone.

On the day of oocyte retrieval, the male partner will produce a semen sample per usual clinic protocol. Following 2-3 hours of incubation, hyaluronidase will be used to denude cumulus cells surrounding oocytes per usual clinic protocol. Fertilization will be performed by intracytoplasmic sperm injection (ICSI) of all mature oocytes by a trained embryologist. After 16-18 hours, fertilization will be evaluated by the existence of two pro-nuclei. Fertilized embryos from each patient's cohort will remain split for culturing in SAGE or Global media systems as previously designated. All embryos will be cultured in the EmbryoScope+ time lapse incubator. Once placed in the EmbryoScope, embryos will be cultured at 37 degrees C with 6% CO2 and 5.5% O2 or up to 6 days without media exchange.

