#### **Statistical Analysis:**

The primary outcome is rate of aneuploidy for embryos cultured in one of two distinct media from the same patient. We will perform a paired t-test to compare number of euploid blastocysts in embryos split for culture in two different media from the same patient. Our secondary outcome is embryo quality for split embryos. Embryo quality will be graded at the cleavage and blastocyst stages. High quality cleavage embryos will have at least 6 blastomeres or greater and scores of "1" or "2" for symmetry and fragmentation. Expanded blastocysts will be considered high quality where inner cell mass and trophectoderm score are "A" or "B." We will perform paired t-tests to compare number of high quality cleavage and blastocyst stage embryos from the cohort of sibling embryos cultured in different media.

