#### **Sample Size Calculation:**

The primary outcome is aneuploid fraction for embryos cultured in two distinct media from the same patient. To detect same difference in euploid fraction as Hickman et al (29% vs 16%) we would need 176 blastocysts per arm. This calculation does not account for clustering of embryos from the same patient; however, we will obtain a substantially higher number of blastocysts per arm as we are planning to power for our secondary outcome (see below).

Our secondary outcome relates to differences in embryo quality among split embryos cultured in distinct media. Previous review of internal data demonstrates that interventions targeting couples with a history of poor embryo quality have been able to demonstrate a four-fold increase in high quality day 3 fraction. We need 62 subjects (31/arm) to detect four-fold increase in high quality day 3 fraction within this population with history of poor embryo quality (< 40% good quality cleavage stage fraction). We estimate that 25% of clinic patients have poor quality cleavage stage fraction. Therefore, we would need  $4 \times 62 = 248$  patients. However, since we are splitting embryos from the same patient, each cohort of embryos serves as its own control. Therefore, we need to enroll **124 patients** to power for our secondary outcome of clinically meaningful differences in embryo quality.

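### The embryo-quality test compares raw numbers of high quality embryos and ignores how many oocytes each ovary supplied, although the outcome was sized on a fraction

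*Combined protocol and SAP*

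**What the plan says.** **Test.** Statistical Analysis says of the two media: "We will perform paired t-tests to compare number of high quality cleavage and blastocyst stage embryos from the cohort of sibling embryos cultured in different". It names no denominator, offset, covariate or weight, and it restricts the test to no subgroup.

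**Allocation.** Study Implementation fixes the medium by ovary: "All oocytes aspirated from the left ovary will be allocated to Global Media while all oocytes from the right ovary will be allocated to SAGE". After ICSI the division stands: "Fertilized embryos from each patient's cohort will remain split for culturing in SAGE or Global media systems as previously designated". Numbers are not rebalanced between the media.

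**Sizing.** The Sample Size Calculation works on a different scale and in a subgroup: "We need 62 subjects (31/arm) to detect four-fold increase in high quality day 3 fraction", among patients whose good quality cleavage fraction is below 40%, taken to be 25% of the clinic. Scaling up and halving for pairing leads to the statement that "we need to enroll 124 patients to power for our secondary outcome of clinically meaningful differences in embryo quality". No section reconciles the sized fraction with the tested number.

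**The concern.** Pairing within a patient removes what both sides share, such as age, sperm and stimulation. It does not remove the difference in how many oocytes the two ovaries gave. A patient with eight oocytes on one side and three on the other will tend to show more high quality embryos on the first side whatever the media do. In a paired t-test on counts, that difference goes straight into the variance of the paired difference.

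The laboratory must know the starting numbers in order to run the split, so the test leaves in noise that could be taken out. Embryo quality is the outcome used to justify 124 patients. A test that carries avoidable variance makes a modest media effect across the cohort easier to miss. The count test also targets a different quantity from the fraction on which the sizing rests.

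**Working it through.** **1. The plan's own figure.** 62 / 0.25 = 4 × 62 = 248, and 248 / 2 = 124. Of 124 patients, 25% is 31, each supplying both arms. The baseline, alpha and power behind 31 per arm are not stated. Assuming two-sided 5%, 80% power and a baseline near 10%, a two-proportion formula without continuity correction gives 32 per arm for 10% vs 40% and 30 per arm for 10.5% vs 42%. So 124 reproduces, and it rests on a fraction.

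**2. Variance added by the split.** Suppose a patient has N embryos, each from either side with probability 1/2 and each high quality with probability p. Let D be the left/right difference in high quality counts.
- Chance split: Var(D) = Np.
- Equal split: Var(D) = Np(1 − p).
- Inflation: 1/(1 − p), which is 1.11 at p = 0.10, 1.67 at 0.40 and 2.0 at 0.50.

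The squared correlation (R²) of D with the difference in embryo numbers is p. For a count taken earlier, p is multiplied by the probability of reaching the embryo stage. Uneven ovaries raise these values.

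**3. Power for a modest effect in all 124 patients.** Assumed inputs, none in the documents: 8 embryos per patient, 0.45 vs 0.54 (mean p = 0.495), 75% fertilisation, 80% maturity.
- Mean of D = (8/2) × 0.09 = 0.36.
- Var(D) ≈ 8 × 0.495 = 3.96, so SD = 1.99 and SE = 1.99/√124 = 0.179.
- Counts: z = 0.36/0.179 = 2.01; power ≈ Φ(2.01 − 1.96) = 52%.
- Adjusting for oocytes retrieved: R² = 0.495 × 0.75 × 0.80 = 0.297; z = 2.01/√0.703 = 2.40; power ≈ 67%.
- Adjusting for mature oocytes: R² = 0.495 × 0.75 = 0.371; z = 2.01/√0.629 = 2.54; power ≈ 72%.

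Simulation with robust standard errors gave about 51%, 65% and 70%, with type I error about 5%.

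**4. The effect the plan was sized on.**

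| Setting | Counts | Adjusted, retrieved | Adjusted, mature |
|---|---|---|---|
| Four-fold effect in the poor-quality quarter, tested in all 124 | about 38% | about 49% | about 53% |
| Four-fold effect, about 31 poor-quality patients only | about 99.5% | – | about 99.8% |

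The first row also depends on the rate assumed in the unaffected patients.

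**5. Analysing the fraction instead.** For 50% vs 60% in all 124 patients and an assumed mean of 6 to 14 embryos, with chance imbalance only, simulated power was 31–71% on counts, 50–88% on unweighted per-patient fractions and 64–97% on a patient-stratified weighted fraction. Unweighted fractions recover only part of the loss. About 3–19% of simulated patients had no embryo in one medium.

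**6. If one ovary yielded more on average.** Assume a 52% share for one side and no media effect. Mean of D = 8 × 0.495 × (0.52 − 0.48) = 0.158, and 0.158/0.179 = 0.89. Two-sided type I error ≈ Φ(−1.07) + Φ(−2.85) ≈ 14%. Simulation gave about 15% for counts and about 5% after adjustment.

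**The case against.** **The count test did not set 124, and the sized effect is safe.** This stands. Enrolment was derived from a fraction in about 31 patients, and for a four-fold effect tested there power is near its ceiling with or without adjustment. A reader might infer that the trial is underpowered for its own sizing target; the documents do not support that. However, the analysis section describes no subgroup test. It compares the whole cohort, and there the loss is material.

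**The planned test is valid.** Under chance imbalance it is, with type I error near 5%. A reader might go further and infer that the fixed left/right allocation makes the count test biased. That requires a systematic difference in oocyte yield between ovaries, and the documents give no figure for one. The 52% share above is illustrative only.

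**The inputs are assumed.** They are. The plan gives neither embryo numbers per patient nor the high quality fraction in the cohort, and its 40% figure is a ceiling for a history of poor quality, not a rate for the trial endpoint. It is tempting to say that adjustment would lift power from 80% to above 90%, but no 80% starting power for this test is stated anywhere.

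**Maturity is not strictly a baseline count.** Oocytes are assigned by ovary at retrieval; incubation, denuding and selection of mature oocytes come afterwards. Whether the media systems already differ at that stage is not described in the available text. This stands and is why oocytes retrieved per ovary belongs in a sensitivity analysis.

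**Conclusion.** The point holds as a loss of efficiency and a mismatch of scale. The plan sizes embryo quality on a fraction, tests it as a raw number in the whole cohort, and takes no account of how many oocytes each ovary supplied. Under the stated assumptions, the whole-cohort test gives up about 14 to 19 points of power for a modest general effect (65 − 51 and 70 − 51) and about 11 to 15 points for a four-fold effect confined to a quarter of patients (49 − 38 and 53 − 38). It gives up almost nothing if the four-fold effect is tested only in the poor-quality patients.

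The direction follows from the design; the size depends on embryo numbers, maturity, fertilisation and quality rates that the plan does not give. No size was worked out for the blastocyst quality count. For the primary count of euploid blastocysts the gain is smaller, under 5 points with an even-chance split, because a smaller share of starting oocytes reaches that endpoint. The change is worth making because it is cheap; the planned test is not invalid under chance imbalance.

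**What to change.** In Statistical Analysis, replace the paired t-tests on numbers of high quality cleavage and blastocyst embryos with a test that accounts for starting number.

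- **Main analysis.** For each patient, regress the between-media difference in high quality count on the between-media difference in mature oocytes injected. Leave the covariate uncentred, so that the intercept is the media difference at equal starting numbers, and test the intercept with robust standard errors.
- **Sensitivity analysis.** Repeat with oocytes retrieved per ovary, the count fixed before allocation to a medium takes effect.
- **Alternative.** Analyse the fraction with a patient-stratified weighted risk difference or a patient-clustered binomial model. This also matches the scale of the sample size calculation. State the denominator and how patients with no embryo in one medium are handled.

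The covariate is available, because Study Implementation says "Fertilization will be performed by intracytoplasmic sperm injection (ICSI) of all mature oocytes by a trained embryologist", so the number per side is known at ICSI. The cost is a sentence or two in the analysis section, one degree of freedom and a linearity assumption. No patients, procedures or data are added. Other left/right confounding from the fixed allocation remains and must be addressed separately.

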#### **Sample Size Calculation:**

The primary outcome is aneuploid fraction for embryos cultured in two distinct media from the same patient. To detect same difference in euploid fraction as Hickman et al (29% vs 16%) we would need 176 blastocysts per arm. This calculation does not account for clustering of embryos from the same patient; however, we will obtain a substantially higher number of blastocysts per arm as we are planning to power for our secondary outcome (see below).

Our secondary outcome relates to differences in embryo quality among split embryos cultured in distinct media. Previous review of internal data demonstrates that interventions targeting couples with a history of poor embryo quality have been able to demonstrate a four-fold increase in high quality day 3 fraction. We need 62 subjects (31/arm) to detect four-fold increase in high quality day 3 fraction within this population with history of poor embryo quality (< 40% good quality cleavage stage fraction). We estimate that 25% of clinic patients have poor quality cleavage stage fraction. Therefore, we would need  $4 \times 62 = 248$  patients. However, since we are splitting embryos from the same patient, each cohort of embryos serves as its own control. Therefore, we need to enroll **124 patients** to power for our secondary outcome of clinically meaningful differences in embryo quality.

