**Specific Aims:**

1. To determine if aneuploidy rates differ between sibling embryos cultured in distinct media.
2. To determine if embryo quality differs between sibling embryos cultured in distinct media.
3. To determine if morphokinetic parameters, as assessed by time lapse imaging, differ between sibling embryos cultured in distinct media.
4. To determine if and how morphokinetic parameters and aneuploidy rates differ between embryos with zona breach performed on day three of embryo development versus at the blastocyst stage.
5. To assess the accuracy of non-invasive genetic testing of embryos from spent culture media.

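### The 124-patient target is derived for day 3 fractions in poor-history patients, but the plan tests numbers of high-quality embryos in all patients, so the power claim is not established for the planned test

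*Combined protocol and SAP*

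**What the plan says.** The Sample Size Calculation section takes its effect size from internal data on couples with poor embryo quality, in whom interventions "have been able to demonstrate a four-fold increase in high quality day 3 fraction". It then states: "We need 62 subjects (31/arm) to detect four-fold increase in high quality day 3 fraction within this population with history of poor embryo quality", with poor quality defined as under 40% good cleavage-stage embryos. It adds: "We estimate that 25% of clinic patients have poor quality cleavage stage fraction". So 62 is multiplied by 4 to give 248, then halved because each patient is her own control. The section concludes that 124 patients are needed "to power for our secondary outcome of clinically meaningful differences in embryo quality", with no limit to a subgroup, stage or scale.

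The Statistical Analysis section plans something else: "We will perform paired t-tests to compare number of high quality cleavage and blastocyst stage embryos from the cohort of sibling embryos". This covers everyone enrolled and agrees with the second aim, "To determine if embryo quality differs between sibling embryos cultured in distinct media". Eligibility does not require a poor-quality history.

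On allocation, Study Implementation says: "All oocytes aspirated from the left ovary will be allocated to Global Media while all oocytes from the right ovary" go to SAGE. The two media can therefore receive different numbers of oocytes within one patient.

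**The concern.** A sample size supports a power claim only for the population, endpoint and test it was computed for. Here the calculation and the test differ in population (poor-history patients against all patients), scale (fraction against number) and stage (day 3 against both cleavage and blastocyst). The section gives no alpha, power, baseline fraction or SD of the paired difference for this outcome, so the claim cannot be carried across from one to the other.

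This calculation fixes the enrolment target. If the whole-cohort test shows no difference, the claim as written invites the reading that a clinically meaningful difference was ruled out with adequate power. The documents do not support that reading.

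The scale matters in its own right. A patient with more embryos in one medium will tend to have more good embryos there even if the media are equivalent. Since side determines medium in every patient, a systematic left-right difference in yield would push all the count differences the same way.

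**Working it through.** **Inputs.** From the Sample Size Calculation section: 31 per arm, 62, 25%, 248, 124. Not given: alpha, power, baseline fraction, embryos per patient, SD of the paired difference. Every such value below is an assumption; all tests are two-sided 5%.

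**1. The plan's own figure.** 2 × 31 = 62; 62 / 0.25 = 248; 248 / 2 = 124. Expected poor-history patients: 124 × 0.25 = 31, each contributing to both media. The chain reproduces and meets its own requirement. The starting 31 cannot be checked. The usual two-proportion formula (80% power, no continuity correction), which treats each patient as one yes/no result, gives 76 per arm for 5% to 20%, 32 for 10% to 40% and 10 for 20% to 80%. So 31 would fit a baseline near 10%. A four-fold rise also requires a baseline of at most 25% (4 × 25% = 100%), although the group is defined by under 40%.

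**2. Calculation and test side by side.**

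| | Calculation | Planned test |
|---|---|---|
| Population | poor-history patients | all enrolled |
| Scale | fraction | number |
| Stage | day 3 | cleavage and blastocyst |
| Structure | two arms, then halved | paired t-test |

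**3. What N alone supports.** For a paired t-test, power = P(|T| > t(0.975, n−1)), where T is noncentral t with noncentrality δ√n and δ = mean / SD of the paired difference. At 80% power, δ = 0.254 for n = 124, 0.294 for n = 93 and 0.52 for n = 31. Conversion to fraction points needs an SD. Simulated SDs of the paired fraction difference (poor-history 10% to 40%, no effect elsewhere) were 0.29 to 0.53, so the detectable difference runs from 0.254 × 0.29 = 0.07 to 0.294 × 0.53 = 0.16, or about 7 to 16 points.

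**4. Power of the planned count test (illustration).** N = 124, a quarter poor-history, others at 40–70%, 2–6 embryos per medium, split equal or Poisson by ovary:

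| Poor-history change | No effect in others | +5 points | +10 points |
|---|---|---|---|
| 10% to 40% | 19–82% | 35% to >99% | 56% to >99% |
| 5% to 20% | 8–37% | 19–92% | 37% to >99% |

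Both rows are four-fold. With no effect in the others, the cohort averages are 0.25 × 30 = 7.5 points and 0.25 × 15 = 3.75 points. So the words four-fold do not fix the power of this test.

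**5. Counts against fractions.** Suppose the media are equivalent, 50% of embryos are high quality, and mean yields are 4.0 and 4.4 (Poisson). Expected counts are 2.0 and 2.2, a difference of 0.2. The SD of the difference is √(2.0 + 2.2) = 2.05, its standard error 2.05 / √124 = 0.184, and z = 0.2 / 0.184 = 1.09. The test rejects with probability P(Z > 1.96 − 1.09) ≈ 0.19. Simulation agrees: 19% on counts, about 5% on fractions. With equal mean yields of 4 and 10% to 40% in the poor-history quarter only, power is 0.32–0.46 on counts and 0.53–0.56 on fractions.

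**6. The poor-history comparison.** Its size is binomial (124, 0.25): 95% range 22 to 41. With 31 pairs, power is 0.87 or more for 10% to 40%. For 5% to 20% it is 0.54–0.72 at 2 embryos per medium, 0.75–0.88 at 3 and about 0.9 at 4.

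**7. Pairs with no fraction in one medium.** If numbers are Poisson with mean m, the proportion is 1 − (1 − e^(−m))²: 25% at m = 2, 9.7% at m = 3, 3.6% at m = 4.

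**The case against.** The plan is more coherent than a list of mismatches suggests. Multiplying by 4 and halving delivers exactly the 31 poor-history patients per medium that the calculation asks for, and 31 pairs in place of 31 per arm is conservative if siblings are positively correlated. On this view, the plan lacks one sentence prespecifying that comparison. The switch between number and fraction may be loose wording too: the primary outcome is also called a rate, a number and a fraction in different places. A null result can be read from its confidence interval, and the detectable difference in SD units follows from N.

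Most of that stands. The arithmetic is sound, and only the conversion from SD units to raw units is missing. What does not follow is the unrestricted claim: the missing sentence is the analysis the number was computed for, and the test actually written down is a different one. Nor is number against fraction only a matter of wording when allocation is by ovary (step 5).

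Three stronger readings are tempting, and the documents support none of them.

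- *The trial is underpowered for embryo quality.* Step 4 spans low to very high power on assumed inputs. The dilution requires no effect in three quarters of patients, which the plan does not say.
- *The poor-history comparison is too small.* The weak figures need 5% to 20% and 2 embryos per medium. The primary calculation counts on more than 176 blastocysts per arm, or 176 / 124 = 1.42 per patient per medium. At 2 embryos, over 1.42 / 2 = 71% would have to reach blastocyst, so 2 is a pessimistic assumption.
- *The primary outcome is affected.* It relies on the blastocysts that 124 patients will yield, and this mismatch does not change that yield.

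**Conclusion.** The mismatch is real and should be corrected, although it concerns a secondary outcome. The calculation and the planned test differ in population, scale and stage, so the assertion that 124 patients power the embryo-quality outcome is not established for that test. The protocol gives no numerical power, so what falls is an assertion, not a figure. Blastocyst quality has no calculation of its own.

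What can be said firmly is the standardised detectable difference in step 3, which needs only N, two-sided 5% and 80% power. The power ranges, the 19% rejection rate and the counts-against-fractions comparison rest on assumed baselines, effects and embryo numbers. They show why the scale and population matter; they do not estimate this trial's power.

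**What to change.** 1. Analyse embryo quality on the fraction scale used in the calculation. Either use the paired within-patient fraction, with a defined denominator and a rule for patients with no embryos in one medium, or an embryo-level model clustered by patient, which keeps those patients.
2. Restate the power claim for the whole-cohort paired analysis: about 0.25 SD detectable at 80% power, two-sided 5%, with all 124 pairs usable, or about 0.29 SD with 93. Convert to fraction points with an SD from internal data. Say that blastocyst quality was not separately powered.
3. If the four-fold figure is kept, limit it to a prespecified poor-history comparison of fractions. Define the history, including how patients without a prior cycle are classified, and give the expected size as about 31, not controlled by design.

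**Cost.** Two paragraphs reworded and one SD estimate from data the sponsor already cites; item 3 adds one baseline item. No extra patients are needed. The power claim becomes narrower. The paired-fraction test would lose about 31, 12 or 5 of 124 pairs at Poisson means of 2, 3 or 4 embryos per medium; the clustered model avoids this loss. Neither choice removes a left-right difference in embryo quality itself, should one exist.

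### The 124 patients are justified by a four-fold rise in a fraction with no stated starting value; that rise is impossible from any start above 25% and across the whole analysed cohort, so the claimed power for clinically meaningful quality differences is unsupported.

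*Combined protocol and SAP*

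**What the plan says.** All of this is in the Sample Size Calculation section unless noted.

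- **Source of the effect.** Internal data on interventions in couples with a poor history, which "have been able to demonstrate a four-fold increase in high quality day 3 fraction".
- **Size.** "We need 62 subjects (31/arm) to detect four-fold increase in high quality day 3 fraction within this population with history of poor embryo quality".
- **Target group.** Defined only by "< 40% good quality cleavage stage fraction".
- **Scaling up.** "We estimate that 25% of clinic patients have poor quality cleavage stage fraction", so 62 is multiplied by 4 to give 248.
- **Halving.** Because "since we are splitting embryos from the same patient, each cohort of embryos serves as its own control", 248 becomes 124.
- **Claim.** The 124 patients are said "to power for our secondary outcome of clinically meaningful differences in embryo quality".

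The section gives no starting or target fraction, SD, alpha, sidedness, power or within-patient correlation. Enrolment is not limited to poor-history couples (Inclusion Criteria). The Statistical Analysis section plans paired t-tests on the number of high quality embryos in the sibling cohort and describes no separate analysis of the poor-history group.

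**The concern.** A ratio is a workable effect size for a fraction only when the starting value is known. Here the start may be anything below 40%, and over part of that range, 25-40%, the stated effect cannot exist. Below 25% the number needed changes several-fold with the start, so 31 per arm cannot be checked against anything in the plan. The effect is also specified for a quarter of the patients, while the planned test uses all of them.

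The 124 is the trial's only enrolment figure. The plan also relies on it when it says that the unadjusted clustering in the primary calculation will be covered by a larger number of blastocysts. If the embryo-quality comparison shows no difference, a reader cannot tell from the protocol what size of difference the trial could have detected.

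**Working it through.** **Inputs.** From the Sample Size Calculation section: ratio 4; 31 per arm; group below 40%; 25% of patients in that group; and, for calibration, 29% vs 16% with 176 blastocysts per arm. Assumed because not stated: two-sided 5% and 80% power, varied below.

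**1. The plan's chain.** 4 × 62 = 248; 248 / 2 = 124; 25% of 124 = 31 poor-history patients, each supplying both arms. This is consistent.

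**2. Which formula the plan probably used.** The two-proportion formula is

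n = [z_α √(2p̄(1−p̄)) + z_β √(p₁(1−p₁) + p₂(1−p₂))]² / (p₁−p₂)²,

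and with continuity correction n′ = (n/4)[1 + √(1 + 4/(n|p₁−p₂|))]². For 16% vs 29% at two-sided 5% and 80% power, n = 160.8 and n′ = 175.8. The corrected form therefore reproduces the plan's 176; the uncorrected form gives 161.

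**3. Ceiling.** 4p ≤ 100% requires p ≤ 25%.

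**4. Number per arm for a four-fold rise** (two-sided 5%, 80% power):

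| Start → target | Uncorrected | Corrected |
|---|---|---|
| 5% → 20% | 76 | 88 |
| 8% → 32% | 43 | 51 |
| 10% → 40% | 32 | 38 |
| 12% → 48% | 25 | 30 |
| 15% → 60% | 17 | 22 |
| 20% → 80% | 10 | 13 |
| above 25% | impossible | impossible |

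**5. Start implied by 31 per arm.** It is 11.6% with the corrected formula and 10.1% uncorrected. Over one- and two-sided tests, 80% and 90% power, and both forms, allowing ±2 per arm, it is about 8-14%. At a fixed 31 per arm, power for a four-fold rise (uncorrected, two-sided 5%) is 43% from a 5% start, 79% from 10% and 97% from 15%.

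**6. The whole cohort.** If 25% of patients are below 40%, then 75% are at 40% or more. Even if every poor-history patient had a fraction of zero, the average would be 0.25 × 0 + 0.75 × 0.40 = 0.30. Four times 30% is 120%, and the largest possible ratio from 30% is 100/30 = 3.3. So a four-fold rise in the average patient fraction cannot occur in the cohort that the paired t-test uses. This bound needs no model. It assumes that enrolled patients resemble clinic patients, as the plan's own multiplication by 4 does, and that past fractions carry over to the study cycle.

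**7. What the planned test detects.** For a paired t-test at two-sided 5% and 80% power, the standardised within-patient difference is 0.25 SD with 124 pairs and 0.52 SD with 31 pairs.

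**8. Illustration only, on the fraction scale.** SD = √(2p(1−p)(1−ρ)/k), with assumed p of 35-60%, ρ of 0.1-0.2 and k of 3-5 embryos per medium, split equally. For p = 0.5, ρ = 0.1, k = 3: SD = √(0.5 × 0.9/3) = 0.387, and 0.2536 × 0.387 = 9.8 points. Over the whole range the result is about 7-10 points for 124 pairs and 14-20 for 31 pairs. The documents give no embryo yield, allocation by left or right ovary will make the splits unequal, and the planned test compares numbers, not fractions.

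**The case against.** The 40% limit classifies individual patients; it is not the group's starting mean. A group selected that way can average well below 25%, and since the internal data are said to have shown a four-fold rise, the mean there must have been 25% or less. For starts of about 12-25%, 31 per arm is enough or more than enough. The 31 may not come from a two-proportion formula at all: a comparison of means gives 31 per arm at a standardised difference of about 0.7. And 31 poor-history pairs among 124 patients is a coherent count. All of this stands. It means that 31 is unverified, not wrong, and that the implied start of 8-14% is conditional on the formula.

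Two stronger readings are tempting, and the documents support neither.

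- **That the poor-history group cannot average as little as 10%.** This needs an assumed distribution of patient fractions. With a beta distribution and 25% of patients below 40%, the group mean is 27-34% at a within-patient correlation of 0.05-0.20, but 17% at 0.50, 10.8% at 0.70 and 7.3% at 0.80. High correlations may be unlikely, but the plan gives no value that excludes them.
- **That the four-fold figure reflects recovery after a poor cycle, which sibling embryos in both media would share.** This would apply only if the internal data were an uncontrolled before-after comparison. The plan does not describe their design.

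Neither the strengths of the plan nor the limits of these readings supplies a starting value, or a link between a four-fold rise in a quarter of patients and a test on all of them.

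**Conclusion.** The concern holds as an unsupported power claim, not as an arithmetic error. Three results carry it. A four-fold rise is impossible from any start above 25%, which covers part of the range the plan allows. If a two-proportion calculation was used, 31 per arm implies a start of about 8-14% (11.6% with the formula that reproduces 176), which the plan neither states nor justifies. In the full cohort the average fraction is at least 30% on the plan's own figures, so the stated effect cannot occur there.

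The first result is free of assumptions. The second depends on the formula and on unstated alpha and power. The third depends on enrolled patients resembling clinic patients, and on treating the good quality fraction in the cut-off and the high quality fraction in the target as the same measure. Nor does the plan say why a four-fold rise, the only quality difference it specifies, would be the smallest that matters clinically. The number 124 may be adequate for a useful difference, but the plan does not show which.

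**What to change.** Keep 124. Delete the four-fold target and the sentence that claims power for clinically meaningful differences. In their place, state the smallest within-patient difference that the planned paired t-test detects at 80% power and two-sided 5%: 0.25 SD for 124 pairs, and 0.52 SD for the expected 31 poor-history pairs if that group is to be examined separately. Convert both to the scale actually tested, at present the number of high quality embryos, using a starting value and an SD of the within-patient difference from the clinic's internal data, and say whether a difference of that size matters clinically. The 7-10 point figure should not be copied in as a result, since it rests on assumed yields and a fraction outcome.

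The cost is a change of wording and a short calculation from internal data of the kind the plan already cites; no extra patients are needed. If those data contain no split cohorts, the SD has to be stated as an assumption with a range. The downside is a less striking target, but one that makes a null result on embryo quality interpretable.
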